5.2.7. Compliance

The site will complete required dosage Preparation Record located in the Study Manual. The use of the Preparation Record is preferred but it does not preclude the use of an existing appropriate clinical site documentation system. The existing clinical site's documentation system should capture all pertinent/required information on the preparation and administration of the dose. This may be used in place of the Preparation Record after approval from the monitor.

At each study visit, the Investigator, or designee, will assess the patient's compliance with the study requirements. The assessment will include checks of protocol compliance and concomitant medication use.

5.3. Drug Storage and Drug Accountability

The investigator, or an approved representative (eg, pharmacist), will ensure that all PF-06650808 is stored in a secure area, under recommended storage conditions and in accordance with applicable regulatory requirements. PF-06650808 should be stored at 2-8°C (36-46°F) and protected from light until ready to use. PF-06650808 should not be frozen. Specific instructions on storage and handling are provided in the DAI located in the Study Manual. To ensure adequate records, all PF-06650808 will be accounted for in the CRF and drug accountability inventory forms as instructed by the sponsor. Unless otherwise authorized by the sponsor, at the end of the clinical trial all drug supplies unallocated or unused must be returned to Pfizer or its appointed agent (eg, a contract research organization [CRO]). If the sponsor authorizes destruction at the trial site, the investigator must ensure that the materials are destroyed in compliance with applicable environmental regulations, institutional policy, and any special instructions provided by the sponsor. Destruction must be adequately documented.

Storage conditions stated in the Investigator Brochure may be superseded by the label storage.

Investigators and site staff are reminded to check temperatures daily (ie, manually or by using alarm systems to alert of any excursions) and ensure that thermometers are working correctly as required for proper storage of investigational products. Any temperature excursions should be reported immediately to the sponsor. The investigational product(s) must be stored as indicated. Deviations from the storage requirements, including any actions taken must be documented and reported to the sponsor. Once a deviation is identified, the investigational product must be quarantined and not used until the sponsor provides documentation to use the investigational product.

Under no circumstances should the investigator or other site personnel supply study drug to other investigators, patients, or clinics, or allow supplies to be used other than directed by this protocol without prior authorization from the sponsor.

5.4. Concomitant Medication(s)

Concomitant treatment considered necessary for the patient's well being may be given at discretion of the treating physician.

Palliative and supportive care for disease related symptoms may be administered at the investigator's discretion and according to any available American Society of Clinical Oncology (ASCO) guidelines. (Anonymous, 2006).²

CCI

All concomitant medications, blood products, as well as non drug interventions (eg, analgesic use or paracentesis) received by patients within 28 days prior to the first dose of study treatment until the Follow-Up Visit will be recorded on the CRF.

5.4.1. Other Anti-tumor/Anti-cancer or Experimental Drugs

No additional anti-tumor therapy including chemotherapy, hormonal therapy, radiotherapy, or experimental anticancer medications will be permitted while patients are receiving study therapy. Additionally, the concurrent use of herbal supplements for an anticancer treatment is not permitted.

Palliative radiotherapy on study is permitted for the treatment of painful bony lesions providing the lesions were known at the time of study entry and the investigator clearly indicates that the need for palliative radiotherapy is not indicative of disease progression.

5.4.2. Supportive care

Palliative and supportive care for disease related symptoms may be administered at the investigator's discretion and according to any available American Society of Clinical Oncology (ASCO) guidelines.

5.4.3. Hematopoietic Growth Factors

Primary prophylactic use of granulocyte-colony stimulating factors is not permitted during the first cycle but they may be used to treat treatment emergent neutropenia as indicated by the current American Society of Clinical Oncology (ASCO) guidelines.

Erythropoietin may be used at the investigator's discretion for the supportive treatment of anemia.

5.4.4. Anti Diarrhea, Anti Emetic Therapy

Primary prophylaxis of diarrhea, nausea and vomiting is permitted in this study at the investigator's discretion. The choice of the prophylactic drug is up to the investigator with sponsor approval and assuming there is no known or expected drug-drug interaction. If so it must be approved by the sponsor.

5.4.5. Corticosteroids

Chronic, systemic corticosteroid use (prednisone \geq 12.5 mg/day or dexamethasone \geq 2 mg/day) for palliative or supportive purpose is not permitted. Acute emergency administration, topical applications, inhaled sprays, eye drops or local injections of corticosteroids are allowed.

5.4.6. Surgery

Caution is advised on theoretical grounds for any surgical procedures during the study. The appropriate interval of time between surgery and PF-06650808 required to minimize the risk of impaired wound healing and bleeding has not been determined. Stopping PF-06650808 is recommended at least 7 days prior to surgery. Postoperatively, the decision to reinitiate PF-06650808 treatment should be based on a clinical assessment of satisfactory wound healing and recovery from surgery.

6. STUDY PROCEDURES

6.1. Screening

All patients being considered for the study and eligible for screening must provide evidence of informed consent for the study before completing any study-specific procedures. A patient identification number will be assigned. The investigator (or appropriate delegate at the site) will obtain informed consent from each patient in accordance with the procedures described in the [Schedule of Activities](#) and [Section Patient Information and Consent](#).

Patients will be screened within 28 days prior to administration of the study treatment to confirm that they meet the patient selection criteria for the study.

For screening procedures see [Schedule of Activities](#) and [Assessments](#) section. Following completion of the screening assessments and confirmation of eligibility, patients may be enrolled.

6.2. Treatment Period

For treatment period procedures, see [Schedule of Activities](#) and [Assessments](#) section.

6.3. Follow-up Visit

For follow-up procedures see [Schedule of Activities](#) and [Assessments](#) section. Patients will return to the clinic at least 28 days, and no more than 35 days, after discontinuation of treatment to undergo review of concomitant medications, performance status, vital signs, and assessment for resolution of any treatment related toxicity. Patients continuing to experience

toxicity at this point following discontinuation of treatment will continue to be followed at least every 4 weeks until resolution or determination, in the clinical judgment of the investigator, that no further improvement is expected.

In the event a patient is unable to return to the clinic for the follow-up visit, telephone contact with the patient to assess adverse events and concomitant medications and treatment is expected. If laboratory assessments are needed to follow-up unresolved adverse events, retrieval of assessments performed at an institution local to the patient is acceptable.

6.4. Patient Withdrawal

The reason for a patient's discontinuation from treatment will be documented in the end of study/withdrawal CRF. Patients will be followed for at least 28 days after the last dose of study drug for adverse events.

Patients may withdraw from treatment at any time at their own request, or they may be withdrawn at the discretion of the investigator or sponsor for safety or behavioral reasons, or the inability of the patient to comply with the protocol required schedule of study visits or procedures at a given study site.

Reasons for withdrawal of study treatment may include:

- Objective disease progression according to RECIST 1.1;
- Global deterioration of health status requiring discontinuation;
- Unacceptable toxicity;
- Pregnancy;
- Adverse Event;
- Medication error without associated adverse event;
- Significant protocol violation;
- Lost to follow-up;
- Patient no longer willing to participate in study;
- Study terminated by Sponsor;
- Death.

Reasons for withdrawal from study follow-up may include:

- Completed study follow-up;
- Study terminated by Sponsor;

- Lost to follow-up;
- Patient refusal for further follow-up;
- Death.

If a patient does not return for a scheduled visit, every effort should be made to contact the patient. All attempts to contact the patient and information received during contact attempts must be documented in the patient's medical record. In any circumstance, every effort should be made to document patient outcome, if possible. The investigator should inquire about the reason for withdrawal, , request the patient to return for a final visit, if applicable, and follow-up with the patient regarding any unresolved adverse events (AEs).

If the patient refuses further visits, the patient withdraws consent for disclosure of future information or for further contact, no further study specific evaluations should be performed, and no additional data should be collected. The sponsor may retain and continue to use any data collected before such withdrawal of consent.

7. ASSESSMENTS

Every effort should be made to ensure that the protocol required tests and procedures are completed as described. However it is anticipated that from time to time there may be circumstances, outside of the control of the investigator, which may make it unfeasible to perform the test. In these cases the investigator will take all steps necessary to ensure the safety and well being of the patient. When a protocol required test cannot be performed the investigator will document the reason for this and any corrective and preventive actions which he/she has taken to ensure that normal processes are adhered to as soon as possible. The study team will be informed of these incidents in a timely fashion.

7.1. Safety Assessment

Safety assessments will include collection of AEs, SAEs, vital signs and physical examination, electrocardiogram (ECG) (12-lead), laboratory assessments, including pregnancy tests and verification of concurrent medications.

7.1.1. Pregnancy Testing

For female patients of childbearing potential, a serum or urine pregnancy test, with sensitivity of at least 25 mIU/mL, will be performed on two occasions prior to starting study therapy – once at the start of screening and once on Day 1 of Cycle 1 before investigator product administration. Following a negative pregnancy result at screening, appropriate contraception must be commenced. Pregnancy tests will also be routinely repeated at every cycle during the active treatment period, at the end of study therapy and additionally whenever one menstrual cycle is missed or when potential pregnancy is otherwise suspected. In the case of a positive hCG test, the patient will be withdrawn from study medication but may remain in the study. Pregnancy tests may also be repeated as per request of IRB/IECs or if required by local regulations.

7.1.2. Adverse Events

Assessment of adverse events will include the type, incidence, severity (graded by the National Cancer Institute Common Terminology Criteria for Adverse Events [NCI CTCAE] version 4.03) timing, seriousness, and relatedness.

Adverse events that occur during the study, including baseline signs and symptoms, will be recorded on the AE CRF page.

7.1.3. Laboratory Safety Assessment

Hematology and blood chemistry will be drawn at the time points described in the [Schedule of Activities](#) and analyzed at local laboratories. On Day 1 of Cycle 1, the hematology and blood chemistry samples do not need to be repeated if the screening assessment is performed within 72 hours prior to dosing. Hematology and blood chemistry will be collected on Day 1, Day 8 and Day 15 of each cycle through Cycle 6. For subsequent cycles, hematology and blood chemistry will be collected on Day 1 of each cycle.

Investigators may have additional blood tests performed for the purpose of planning treatment administration, dose modification, or following AEs.

Hematology	Chemistry*	Coagulation	Urinalysis	Pregnancy Test
Hemoglobin	ALT/SGPT	PT or INR	Urine dipstick	For female patients of childbearing potential, serum or urine
Platelets	AST/SGOT	PTT	For urine protein: If $\geq 2+$ protein on urine dipstick, then collect spot urine sample to calculate urine protein to creatinine ratio (UPCR)	
WBC	Alk Phos		Microscopic analysis if dipstick abnormal	
Absolute Neutrophils	Sodium			
Absolute Lymphocytes	Potassium			
Absolute Monocytes	Magnesium			
Absolute Eosinophils	Chloride			
Absolute Basophils	Calcium			
	Total Bilirubin*			
	Total protein			
	BUN or Urea			
	Creatinine			
	Uric Acid			
	Glucose (non-fasted)			
	Albumin			
	Phosphorous			
	Bicarbonate or carbon dioxide			
	LDH			

* For Hy's law potential cases, in addition to repeating AST and ALT, laboratory tests should include albumin, creatine kinase, total bilirubin, direct and indirect bilirubin, gamma-glutamyl transferase, prothrombin time (PT)/INR, and alkaline phosphatase.

7.1.4. Vital Signs and Physical Examination

Patients will have a physical exam to include weight, vital signs, assessment of ECOG status and height; height will be measured at screening only.

A complete physical examination (PE) will be performed at Screening, Day 1 of Cycle 1, and at the End of Treatment visit for each patient and will include an assessment of all body systems (including neurological examination, genitourinary examination is optional), the measurement of body weight, vital signs and assessment of ECOG performance status. The complete PE on Day 1 of Cycle 1 is not required if the screening complete PE is performed within 72 hours of dosing. Findings of all physical examinations should be recorded in the source documents, and any change from baseline considered by the investigator to be clinically significant should be recorded as an adverse event in the CRF.

Abbreviated PEs, including skin assessment, should be performed as appropriate at each visit where complete physical exams are not required, and on an as needed basis for assessment of adverse events. Abbreviated exams should be targeted to specific symptoms or complaints and be consistent with local standard of care.

Weight and body surface area (BSA) do not need to be performed at each visit; however patients should be monitored throughout the study for significant weight change. If, in the Investigator's opinion, clinically significant weight change occurs, BSA should be recalculated to determine appropriate dose.

Vital signs will include measurements of blood pressure, pulse rate and temperature (oral, tympanic or axillary). On Day 1 of each cycle, vital signs should be measured prior to infusion start (pre-dose) and 1 hour after the start of the infusion. Sitting blood pressure (BP) will be measured with the patient's arm supported at the level of the heart and recorded to the nearest mmHg sufficient. The same arm (preferably the dominant arm) should preferably be used throughout the trial. The blood pressure cuff, which has been properly sized and calibrated, should be used to measure blood pressure. The use of automated devices for measuring BP and pulse rate is acceptable. When the timing of the measurements coincides with a blood collection, blood pressure and pulse rate should be obtained prior to the nominal time of the blood collection.

7.1.5. (12-Lead) ECG

12-lead ECG will be collected as per the [Schedule of Activities](#) and should be performed after the patient has rested quietly for at least 10 minutes. ECGs will be compared to the patient's screening ECG and any clinically significant changes will be recorded as adverse events and evaluated further, as clinically warranted. If the mean QTc is prolonged (value of >500 msec), the ECGs should be re-evaluated by a qualified person at the institution for confirmation. Additional ECGs should be performed if clinically indicated.

If patient experiences a cardiac or neurologic AE (specifically syncope, dizziness, seizures, or stroke), an ECG (triplicate) should be obtained at the time of the event.

When matched with PK sampling, the ECG should preferably be carried out before or after each PK sample drawing such that the PK sample is collected at the nominal time (ie, the timing of the PK collections over rides the timing of the ECG collections).

7.2. Pharmacokinetics Assessments

7.2.1. Blood for PK analysis of PF-06650808, Total Antibody (PF-06460005); and Unconjugated Payload (PF-06380101)

Blood samples (4 mL of whole blood for PK analysis of unconjugated payload (PF-06380101) analysis and 6 mL of whole blood for PK analysis of ADC (PF-06650808) and total antibody (PF-06460005) will be collected in appropriately labeled tubes at times specified in the [Schedule of Activities](#). PK sampling schedule may be modified based on emerging PK data.

In addition to samples collected at the scheduled times, an additional blood sample should be collected from patients experiencing unexpected and/or serious AE's and the date and time documented in the CRF.

All efforts will be made to obtain the PK samples at the scheduled nominal time relative to dosing. However, samples obtained within 10% of the nominal time (eg within 6 minutes of a 60 minute sample) will be considered protocol compliant, and the exact time of the sample collection noted on the CRF. If a scheduled blood sample collection cannot be completed for any reason, the missed sample time may be re-scheduled with agreement of clinical investigators, patient and Sponsor.

CCI

[figure not shown]
[figure not shown]

CCI

. Samples collected for this purpose will be retained in accordance to local regulations and if not consumed during the course of these experiments, will be discarded.

CCI

7.4. Tumor Response Assessments

Tumor assessments will include all known or suspected disease sites. Imaging may include chest, abdomen and pelvis computed tomography (CT) or magnetic resonance imaging (MRI) scans; brain CT or MRI scan for patients with known or suspected brain metastases; bone scan and/or bone X-rays for patients with known or suspected bone metastases. Baseline CNS imaging is not required with the exception of symptomatic patients to rule out central nervous system (CNS) metastases.

The same imaging technique used to characterize each identified and reported lesion at baseline will be employed in the subsequent tumor assessments.

Anti-tumor activity will be assessed through radiological tumor assessments conducted at baseline, during treatment as specified in the [Schedule of Activity](#), whenever disease progression is suspected (eg, symptomatic deterioration), and at the time of withdrawal from treatment (if not done in the previous 6 weeks).

Assessment of response will be made using RECIST version 1.1 ([Appendix 2](#)). Changes in tumor size will be categorized as complete response (CR), partial response (PR), stable disease (SD), or progressive disease (PD), the latter incorporating the appearance of new lesions. For patients in Part 2, responses of CR or PR must be confirmed by repeat assessment no more than 4 weeks after the criteria for response are first met.

All patients' files and radiologic images must be available for source verification and for potential peer review.

CCI

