15. **Registration:** Patient number and dose level allocation will be provided by Pfizer Inc. Treatment should begin no longer than 3 days from registration.
16. **Study Treatment:** PF-06650808 will be administered once every 21 days as an infusion over approximately 60 minutes.
17. **Tumor Assessments:** Tumor assessments will include all known or suspected disease sites and may include chest, abdomen and pelvis CT or MRI scans. Brain scans and bone scans should be performed at baseline if disease is suspected and on-study as appropriate to follow disease. Baseline CNS imaging is not required with the exception of symptomatic patients to rule out CNS metastases. CT or MRI scans are to be done every 6 weeks (± 5 days) for the first two assessments (Week 6 and Week 12) and will then be collected every 12 weeks thereafter until disease progression by RECIST (v1.1) or death, or until permanent discontinuation of study treatment. Tumor assessments should be fixed according to the calendar, regardless of treatment delays. For patients enrolled in Part 2, responses of CR or PR must be confirmed by repeat assessment no more than 4 weeks after the criteria for response are first met. Tumor assessments should be repeated at the End of Treatment visit if more than 6 weeks have passed since the last evaluation.

CCI

19. **Anti PF-06650808 Antibodies:** Collection of serum to detect the presence of antibodies to PF-06650808 is to be obtained prior to the start of study drug infusion. Patients having an unresolved adverse event that is possibly related to anti-PF-06650808 antibodies at their last assessment will be asked to return to the clinic for ADA and drug concentration blood sampling at up to 3 month intervals until the adverse event or its sequelae resolve or stabilize at a level acceptable to the investigator and sponsor.

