2.2. Endpoints

Primary Endpoint (Part 1)

- First cycle Dose Limiting Toxicities (DLTs) in order to determine the MTD and RP2D.

Primary Endpoint (Part 2)

- Response rate (RR) as determined by the Response Evaluation Criteria in Solid Tumor (RECIST) version 1.1 criteria.

Secondary Endpoints

- Adverse Events (AEs) as characterized by type, frequency, severity (as graded by NCI CTCAE v.4.03), timing, seriousness and relationship to study treatment.
- Laboratory abnormalities as characterized by type, frequency, severity (as graded by NCI CTCAE v. 4.03) and timing.
- Vital Signs.
- Systemic pharmacokinetic (PK) exposure of ADC (PF-06650808), total antibody (PF-06460005) and unconjugated payload (PF-06380101) will be determined with validated methods. Standard noncompartmental PK parameters will be determined from the respective concentration-time data.
- Immunogenicity of ADC (PF-06650808); Human serum ADA (anti-PF-06650808 antibody) samples will be analyzed for the presence or absence of anti-PF-06650808 antibodies, following a tiered approach using screening, confirmation and titer/quantitation.
- Objective tumor response, as assessed using the Response Evaluation Criteria in Solid Tumor (RECIST) version 1.1 by calculating the Overall Response Rate (ORR), Progression Free Survival (PFS), and Overall Survival (OS) – Part 2 only.

CCI [REDACTED]

- CCI [REDACTED]
- CCI [REDACTED]
- CCI [REDACTED].
- CCI [REDACTED]

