3. STUDY DESIGN

3.1. Study Overview

This is a Phase 1, open label, multi-center, single arm, non randomized, multiple dose, safety, PK and PD study of single agent PF-06650808 in sequential cohorts of adult patients with advanced solid tumors for whom no standard therapy is available. Successive cohorts of patients will receive escalating doses of PF-06650808 intravenously every 21 days starting at a dose of 0.2 mg/kg.

The proposed doses, schedule(s) and PK timepoints may be reconsidered and amended during the study based on the emerging safety and PK data.

Approximately 55 patients are expected to be enrolled in the study at approximately 3-4 sites. The actual number of patients enrolled will depend upon tolerability of PF-06650808 and the number of dose levels required to identify the MTD.

Patients will participate in the study for approximately 6 months. This includes a 28 days screening period and approximately 4 month treatment period and a 28 day post dose follow-up period. Treatment with study drug will continue until: disease progression, patient refusal or unacceptable toxicity occurs. Patients who demonstrate clinical benefit with manageable toxicity and are willing to continue receiving the study treatment will be given the opportunity to continue treatment upon agreement between investigator and sponsor. Therefore, participation may be longer than 6 months for some patients.

The study will include two parts, a dose escalation phase (Part 1) followed by a dose expansion phase (Part 2). Part 1 will estimate the MTD in dose escalation cohorts in patients with advanced solid tumors for whom no standard therapy is available in order to establish the RP2D. Part 2 will include approximately 20 patients with TNBC enrolled at the MTD in order to explore benefit from treatment as suggested by preclinical findings by providing an estimate of the likely response rate in this patient population and will better define the safety profile at the RP2D. Additional safety information gathered in Part 2 may be used to modify the dose recommended for future Phase 2 studies.

The study is expected to be completed in approximately 24 months. The end of the study is the last visit of the last patient.

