9.4.1. Analysis of Overall Response

For patients to be considered evaluable for efficacy they must have received at least one dose of study medication and have a baseline tumor assessment. Patients must also present with measureable disease.

The best overall response is the best response recorded from first dose until disease progression/recurrence (taking as reference for PD the smallest measurements recorded since screening). In general, the patient's best response assignment will depend on the achievement of both measurement and confirmation criteria. All measurements (or "too small to measure") must be provided for every target lesion to document SD or PR.

The main goal of confirmation of objective response is to avoid an incorrect estimation of the response rate observed. In cases where confirmation of response is not feasible, it should be made clear when reporting the outcome of such studies that the responses are not confirmed.

To be assigned a status of PR or CR, changes in tumor measurements must be confirmed by repeat assessments that should be performed no less than 4 weeks after the criteria for response are first met. Clinical benefit response (CBR) is defined as a CR, PR or SD ≥ 6 cycles.

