## 7. ENDPOINTS AND COVARIATES

### 7.1. Efficacy Endpoint(s)

*Objective tumor response, as assessed using the Response Evaluation Criteria in Solid Tumor (RECIST) version 1.1 by calculating the Overall Response Rate (ORR), Progression Free Survival (PFS), and Overall Survival (OS).*

All efficacy endpoints are secondary in this study, which include objective tumor response, progression-free survival (PFS), and overall survival (OS) in the expansion cohort. The above efficacy endpoints are derived based on the disease response per investigator evaluation on the CRF pages, which is the primary method of documentation of disease.

- **Overall Response (OR)** – is defined as confirmed complete response (CR) or confirmed partial response (PR) according to RECIST 1.1 ([Appendix 2](#)). Confirmed responses are those that persist on repeat imaging study at least 4 weeks after the initial documentation of response. Patients who do not have on-study radiographic tumor re-evaluation, who receive anti-tumor treatment other than the study medication prior to reaching a CR or PR, or who die, progress, or drop out for any reason prior to reaching a CR or PR will not

be counted as responders in the assessment of OR. Clinical benefit response (CBR) is defined as a CR, PR or SD  $\geq 6$  cycles.

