### **Best overall response**

The best overall response is defined according to the tumor response along the study. Complete or partial responses may be claimed only if the criteria for each are met at a following time point as specified in the protocol (generally 4 weeks later). In this circumstance, the best overall response can be interpreted as in [Table 2](#).

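### Sites are told to confirm Part 2 responses within 4 weeks, but the analysis accepts only confirmation at 4 weeks or later

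*Protocol*

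**What the plan says.** Two protocol passages give the scan instruction for Part 2. Protocol 7.4 and Schedule of Activities footnote 17 both state that "responses of CR or PR must be confirmed by repeat assessment no more than 4 weeks after the criteria for response are first met". Here 4 weeks is a maximum.

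Two passages define the response that is analysed. Protocol 9.4.1 says that, for PR or CR to be assigned, changes in tumour measurements "must be confirmed by repeat assessments that should be performed no less than 4 weeks after the criteria for response are first met". SAP 7.1 counts only confirmed CR or PR and adds: "Confirmed responses are those that persist on repeat imaging study at least 4 weeks after the initial documentation of response". Here 4 weeks is a minimum.

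SAP Appendix 2 (Best overall response) asks for the criteria to be "met at a following time point as specified in the protocol (generally 4 weeks later"), which sends the reader back to the protocol.

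Footnote 17 also sets the routine scans: Weeks 6 and 12, each within 5 days, then every 12 weeks until progression, death or permanent discontinuation of treatment. It adds: "Tumor assessments should be repeated at the End of Treatment visit if more than 6 weeks have passed since the last evaluation".

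Protocol 2.2 gives the Part 2 primary endpoint as "Response rate (RR) as determined by the Response Evaluation Criteria in Solid Tumor (RECIST) version 1.1 criteria". SAP 7.1 says instead that "All efficacy endpoints are secondary in this study".

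**The concern.** The maximum stands in the text that tells sites when to scan, and the minimum stands in the text that decides which scans count. A site that rescans a responder at 2 or 3 weeks has followed its instructions, yet its scan cannot confirm the response under Protocol 9.4.1 or SAP 7.1. The response then depends on some later scan at 4 weeks or more, which may not be required or may come after the response has ended.

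Whichever label it carries, the response rate is the main activity estimate from Part 2, and it rests on about 20 patients. A scan that was never taken cannot be recovered at analysis.

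**Working it through.** The plan states no figure to reproduce: Protocol 9.3 says the Part 2 size has no statistical justification, and no response rate or duration is assumed. The check therefore covers windows, scan gaps and the effect on the rate.

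**1. Overlap of the two rules** (days after first response)
- Scan instruction: day 1 to day 28.
- Analysis definition: day 28 onward.
- Both satisfied: day 28 only. Days 1 to 27 satisfy the instruction and fail the definition.

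**2. Can a routine scan confirm instead?**
- Week 6 to Week 12: 6 × 7 = 42 days. With 5 days' tolerance on each scan, the range is 32 to 52. This meets the minimum.
- Week 12 to Week 24: 12 × 7 = 84 days (74 to 94 if the same tolerance is assumed). This meets the minimum, but only if the patient is still on treatment and still in response.

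**3. Example: first response at Week 12 (day 84), repeat scan at Week 15 (day 105)**
- The repeat is at 105 − 84 = 21 days: valid for the site, not for the analysis.
- The earliest scan that could confirm is on day 84 + 28 = 112.
- The End of Treatment scan is required only when more than 42 days have passed since the last scan. With the early repeat, that means after day 105 + 42 = 147. Without it, after day 84 + 42 = 126.

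So if treatment stops on days 105 to 147, no further scan is required and none meets the minimum. The cause differs by stopping day:

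| Treatment stops | Why the response is unconfirmed |
|---|---|
| Days 105–111 | Fewer than 28 days since first response; a repeat timed at 4 weeks would not yet have been due |
| Days 112–126 | The dedicated repeat was taken too early; at 4 weeks it could have confirmed |
| Days 127–147 | The early repeat also removed an End of Treatment scan that would otherwise have been required |

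Protocol 3.1 plans an "approximately 4 month treatment period", which is 4 × 30.44 ≈ 122 days and falls in the middle row. Responders may stay on longer.

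**4. Effect on the rate.** One patient in 20 is 5 percentage points. Exact (Clopper-Pearson) intervals, in line with the exact method in SAP 9.1:

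| Confirmed | Rate | 95% CI |
|---|---|---|
| 4/20 | 20% | 5.7–43.7 |
| 3/20 | 15% | 3.2–37.9 |
| 2/20 | 10% | 1.2–31.7 |
| 1/20 | 5% | 0.1–24.9 |
| 0/20 | 0% | 0–16.8 |

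The counts are illustrative; falling from 4 to 0 is the worst case.

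**5. How often would a routine scan miss the response?** Assume exponential response duration with median m weeks, m from 8 to 24 (my assumption). Take responses still present at 4 weeks, whose only later scan is the next routine one.
- First response at Week 6, next scan 6 weeks later: the probability of persisting is 0.5^(2/m) = 84.1% (m = 8), 89.1% (12), 94.4% (24). Lost: 6 to 16%.
- First response at Week 12 or later, next scan 12 weeks later: 0.5^(8/m) = 50.0%, 63.0%, 79.4%. Lost: 21 to 50%.

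Four such responders in 20 would give 20% if confirmed at 4 weeks. Relying on routine scans, the expected number confirmed is 3.36 to 3.78 (16.8 to 18.9%) if all first respond at Week 6, and 2.00 to 3.17 (10.0 to 15.9%) if all do so at Week 12 or later. Stopping treatment early would add to the loss.

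**The case against.** The strongest reply is that this is a wording slip with limited consequences. Protocol 9.4.1 nearly repeats the sentence in 7.4 with the direction reversed, and sites hold both sections. The study tests no hypotheses (SAP 4.1 and 9.1), and no decision threshold on response rate appears in the visible text. Protocol 9.4.1 asks that unconfirmed responses be reported as such, and Protocol 9.4 and SAP 9.2.2.1 provide listings, so these patients would be visible. A Week 6 responder is scanned again at Week 12 anyway. The duration model rests on values the documents do not give, and its larger losses need every responder to respond late and every site to rescan before day 28.

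Much of this stands as a limit on size. Loss is not automatic, the modelled rates are illustrations, and in the example the restarted 6-week clock adds loss only on days 127 to 147. None of it removes the conflict: labelling a response as unconfirmed does not put it into the confirmed rate.

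It is also fair that an analyst might count an early repeat. Table 2 of SAP Appendix 2 turns PR followed by PR into PR with no interval, and the text above that table defers to the protocol. This makes matters worse, because the same scans could then yield two different response rates.

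**Conclusion.** The concern holds. The protocol contradicts itself on when a Part 2 response must be confirmed, SAP 7.1 sides with the minimum, and nothing in either document says which rule prevails. Sites that follow Protocol 7.4 exactly can produce scans that the definition of the protocol's own Part 2 primary endpoint rejects. This must be corrected.

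The firm results are the day-28-only overlap and 5 points per lost responder at n = 20. The likely number lost is not known. It depends on when responses first appear, how long they last, when treatment stops and how early sites rescan, and the documents quantify none of these for responders. Exposure is greatest for first responses at Week 12 or later.

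**What to change.** - In footnote 17 and Protocol 7.4, change the limit from no more than to no less than 4 weeks, matching Protocol 9.4.1 and SAP 7.1.
- Keep the dedicated repeat scan and give it an upper window, for example the 5-day tolerance footnote 17 already uses for routine scans, so that responders at Week 12 or later do not wait 12 weeks. This part is a design choice, separable from the correction itself.
- State that a routine scan at 4 weeks or later also confirms. SAP 7.1 already allows this by its wording; saying so removes doubt.
- In SAP Appendix 2, replace the approximate interval with the same rule.

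The cost is a few words in two protocol passages and one SAP passage. The protocol change is an amendment and needs prospective IRB/IEC approval (Protocol 12.1). No scan is added, because the repeat scan is already required and only moves later.
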